##### **Maintenance Phase**

Four weeks after completing the TEMODAL® + RT (Radiotherapy) phase, TEMODAL® is administered for an additional 6 cycles of maintenance treatment. Dosage in Cycle 1 (maintenance) is 150 mg/m^2 once daily for 5 days followed by 23 days without treatment. At the start of Cycle 2, the dose is escalated to 200 mg/m^2, if the CTC non-hematologic toxicity for Cycle 1 is Grade  $\leq 2$  (except for alopecia, nausea and vomiting), absolute neutrophil count (ANC) is  $\geq 1.5 \times 10^9/L$ , and the platelet count is  $\geq 100 \times 10^9/L$ . If the dose was not escalated at Cycle 2, escalation should not be done in subsequent cycles. The dose remains at 200 mg/m^2 per day for the first 5 days of each subsequent cycle except if toxicity occurs. Dose reductions during the maintenance phase should be applied according to Tables 8 and 9. During treatment a complete blood count should be obtained on day 22 (21 days after the first dose of TEMODAL®). The TEMODAL® dose should be reduced or discontinued according to Table 9.

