## **4. STUDY DESIGN**

### **4.1. Overview of Study Design**

This is a single center, phase 2, open label, open-ended, add-on, single dose study of maximum duration of 260 weeks in patients receiving standard therapy for newly diagnosed GBM. In total 30 patients who meet the entry criteria will be entered into the study within 3 weeks of finishing their last day of combined radiotherapy/temozolomide. Avelumab will be initiated concurrently with the initiation of the first 5 days, monthly cycle of temozolomide.

The study will consist of 3 different phases: Combination Phase a Monotherapy Phase and an Extended Safety Follow-up Phase.

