### **4.2. Treatment Phases of the Study**

**Combination Phase:** Upon completion of the standard combination therapy of radiotherapy (total dose 60 Gy, administered as daily 2Gy fractions, 5 days/week or as per local standard) and temozolomide (75 mg/m^2/day p.o. qd) and a treatment break of no more than 21 days, the combination phase will start. Patients will receive temozolomide and avelumab for 6 cycles of 28 days each. During the 1st cycle Temozolomide will be given the first 5 days at a dose of 150mg/m^2/day p.o. In the next cycle, the temozolomide dose should be escalated to 200/mg/m^2 if permitted by the patient's hematological and non-hematological toxicity profile (as per NCI-CTC AE version 5). The temozolomide dose will be adjusted according to hematological and non-hematological toxicity as per temozolomide's product monograph (appendix 4). Avelumab will be administered on day 1 and day 15 of each cycle at a dose of 10mg/kg IV. Avelumab therapy will be withheld according to the occurrence and severity of avelumab emergent adverse events as per table 3. Patients will continue the

combination of temozolomide (150 – 200mg/m^2 per day PO X5 days Q28days) and avelumab (at 10mg/kg dose, IV on days 1 and 15 per cycle) until 6 cycles are completed or until the occurrence of a termination event.

**Monotherapy Phase:** Upon completion of the Combination Phase or upon stopping temozolomide because of temozolomide related toxicity/tolerability issues or patient choice, the patient will continue into the avelumab Monotherapy Phase. Avelumab 10mg/kg IV Q2weeks will be continued as monotherapy until the occurrence of a termination event defined as one of the following: 1) clinical evidence of neurological deterioration resulting in an ECOG score of at least 3 or more, unexplained by other comorbidities, unchanged by an increase in corticosteroid dose and sustained for at least two weeks or 2) treatment emergent adverse event (TEAE) of grade 3 or more or 3) withdrawal of patient consent.

Patients who experience irAE's may according to table 3 directives have their avelumab therapy suspended.

The use of Bevacizumab or re-irradiation will not be allowed in the study and will be considered as evidence of a termination event.

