## 7.2. Exclusion Criteria

1. Patients who have evidence of leptomeningeal disease
2. Known significant pulmonary, cardiovascular, hepatic disorders or any other disease that in the opinion of the investigator would be contraindicated to receive anti PD-L1 therapy such as avelumab,
3. "Clinically significant (i.e., active) cardiovascular disease: cerebral vascular accident/stroke (< 6 months prior to enrollment), myocardial infarction (< 6 months prior to enrollment), unstable angina, congestive heart failure ( $\geq$  New York Heart Association Classification Class II), or serious cardiac arrhythmia requiring medication."
4. Prior treatment with bevacizumab or any checkpoint immune blockade therapies
5. Any other concomitant immunosuppressant other than temozolomide and steroids or any recent (within 3 months) experimental therapy
6. Patients who have finished their radiotherapy course more than 3 weeks prior to baseline
7. Prior organ transplantation, including allogeneic stem-cell transplantation
8. Significant acute or chronic infections including, among others:
  - Known history of testing positive test for human immunodeficiency virus (HIV) or known acquired immunodeficiency syndrome (AIDS),

- Positive test for HBV surface antigen and / or confirmatory HCV RNA (if anti-HCV antibody tested positive),
- 9. Active autoimmune disease that require ongoing corticosteroid and/or immunosuppressant therapy that might deteriorate when receiving an immunostimulatory agent:
  - Subjects with diabetes type I, vitiligo, psoriasis, hypo- or hyperthyroid disease or any other autoimmune disease not requiring immunosuppressive treatment are at the investigator's discretion eligible
  - Subjects requiring hormone replacement with corticosteroids are eligible if the steroids are administered only for the purpose of hormonal replacement and at doses  $\leq$  10 mg or 10 mg equivalent prednisone per day
  - Administration of steroids through a route known to result in a minimal systemic exposure (topical, intranasal, intro-ocular, or inhalation) are acceptable
- 10. Known severe hypersensitivity reactions to monoclonal antibodies (Grade  $\geq$  3 NCI-CTCAE v 4.03), any history of anaphylaxis, or uncontrolled asthma (that is, 3 or more features of partially controlled asthma)
- 11. Pregnancy or lactation
- 12. Known alcohol or drug abuse
- 13. Any psychiatric or cognitive condition that would prohibit the understanding or rendering of informed consent

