## **9.2. Procedures for Enrolment of Eligible Subjects**

Once a subject has fulfilled the entry criteria a subject Enrolment and Identification Code will be attributed and inscribed in the Enrolment and Identification Code List. The latter must be maintained by the investigator.

Baseline evaluation and start of treatment should occur on the same day. When this is not feasible, the delay between baseline evaluation and start of treatment must be kept to a minimum and should not exceed 7 days.

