**Table 1: STUDY ACTIVITIES**

Tests and Evaluations	Screening Visit	Combination/ phase Week 0 to 24 Visit window: $\pm 2$ days														Monotherapy phase Week 26 to 52  Visit window: $\pm 2$ days														Extended safety follow-up phase 
		0	2	4	6	8	10	12	14	16	18	20	22	24	26	28	30	32	34	36	38	40	42	44	46	48	50	52		
Week	-12 to -1	0													26	28	30	32	34	36	38	40	42	44	46	48	50	52	EOS	
Informed Consent	X																													
Demographics Medical History	X																													
Physical Exam	X	X		X		X		X							X					X					X			X	X	
Neurological Exam	X	X		X		X		X							X					X					X			X	X	
Karnofsky	X	X																												
Vital Sign	X	X	X	X	X	X	X	X	X	X	X	X	X	X	X	X	X	X	X	X	X	X	X	X	X	X	X			
Lab's 	X	X	X	X	X	X	X	X	X	X	X	X	X	X	X	X	X	X	X	X	X	X	X	X	X	X	X			
ECOG	X	X	X	X	X	X	X	X	X	X	X	X	X	X	X	X	X	X	X	X	X	X	X	X	X	X	X			
MRI or CT scan		X																											X	X
P300		X																											X	X
AE's and concomitant medications		X	X	X	X	X	X	X	X	X	X	X	X	X	X	X	X	X	X	X	X	X	X	X	X	X	X	X		
Pre-infusion questionnaire		X	X	X	X	X	X	X	X	X	X	X	X	X	X	X	X	X	X	X	X	X	X	X	X	X	X			
Avelumab infusion Q 2 weeks		X	X	X	X	X	X	X	X	X	X	X	X	X	X	X	X	X	X	X	X	X	X	X	X	X	X			
Temozolamide		X		X		X		X		X		X		X		X		X		X		X		X		X				

See foot note on the next page

- 1 The Extended Safety phase will involve a site visit at day 30 and telephone follow-up at day 60 and 90 post end of treatment. A second site visit may be required if there is any concern
2. Patients who withdraw prematurely from the treatment or complete the 260 weeks of treatment will be offered to enter the Extended safety follow-up phase
3. Lab's: **Hematology** will include Hemoglobin, platelet count, WBC count, absolute neutrophils, and lymphocytes. **Coagulation** will include INR, and aPTT (at screening or baseline only). **Blood chemistry** will include total bilirubin, AST, ALT, LDH, alkaline phosphatase, serum albumin, phosphate, serum creatinine, and electrolytes (sodium, potassium, calcium), glucose, amylase, lipase, TSH, GGT, CK. **Urinalysis** will include urine dipstick test. **Serum  $\beta$ -HCG** must be performed at screening in women of childbearing potential. Subsequent **urine  $\beta$ -HCG** must be collected monthly. Additional tests may be done at the discretion of the investigator for patient safety.
- TSH T4 will be collected Q8weeks and repeated at the Extended Safety visit

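### The temozolomide row of Table 1 carries 13 four-weekly marks running into the Monotherapy Phase, while the protocol text gives six cycles; the start interval in Appendix 4 also needs reconciling with 4.2

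*Protocol*

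**What the plan says.** **Number of cycles.** Protocol 4.2 states: "Patients will receive temozolomide and avelumab for 6 cycles of 28 days each". Avelumab then continues alone until a termination event. The Synopsis, 10.1 (dose and schedule), 10.3 (temozolomide) and the monograph extract in Appendix 4 all give the same count of six.

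**Table 1.** Section 9 refers the reader to Table 1 for the type and timing of assessments. The table heads its columns as a Combination Phase for weeks 0 to 24 and then "Monotherapy phase Week 26 to 52". Its temozolomide row carries 13 marks, each separated from the next by one empty two-weekly column. No footnote to the table limits temozolomide to six cycles.

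**Start of maintenance.** Under 4.2, after chemoradiation and "a treatment break of no more than 21 days, the combination phase will start". Section 4.1 ties the two drugs together: "Avelumab will be initiated concurrently with the initiation of the first 5 days, monthly cycle of temozolomide". Exclusion criterion 6 in 7.2 applies the same limit up to the baseline visit: "Patients who have finished their radiotherapy course more than 3 weeks prior to baseline". Section 9.2 allows a gap between that visit and treatment: "the delay between baseline evaluation and start of treatment must be kept to a minimum and should not exceed 7 days". The Maintenance Phase paragraph of Appendix 4 instead begins "Four weeks after completing the TEMODAL" plus radiotherapy phase.

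**What Appendix 4 is cited for.** In 4.2 it is toxicity: "The temozolomide dose will be adjusted according to hematological and non-hematological toxicity as per temozolomide's product monograph (appendix 4"). Section 10.1 cites it for adjusting or withholding the dose. Neither cites it for the start date.

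**The concern.** Table 1 is what site staff are likely to schedule from, and for temozolomide it disagrees with every statement in the text. Marks beyond week 24 would have temozolomide given in the phase that 4.2 defines as avelumab monotherapy.

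This matters for exposure to a cytotoxic drug, and it also reaches the primary endpoint. Protocol 12.3.1 and SAP 1.3.1 base that endpoint on avelumab-related adverse events that lead to permanent or transient discontinuation. Section 11.1.3 asks the investigator to judge relatedness separately for temozolomide and avelumab. The note in 9.3.4 says that Grade 3 or higher events due to temozolomide are not a reason to withhold avelumab. Which drug an event is assigned to therefore affects both the handling of the patient and the endpoint count, and that judgement is harder while both drugs are being given.

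Two exploratory covariates also presuppose one agreed schedule: cumulative temozolomide dose (5.3), and the extent to which the six cycles are completed (12.3.3 and SAP 1.3.3).

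The start interval is a lesser matter. A reader who takes Appendix 4 as part of the study schedule finds a different waiting time from the one in 4.2.

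**Working it through.** No power or sample-size formula applies. The check is a count and calendar arithmetic.

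**1. The text's own figure.** Inputs from 4.2: 6 cycles of 28 days. 6 × 28 = 168 days, and 168 / 7 = 24 weeks. Cycle starts fall at weeks 0, 4, 8, 12, 16 and 20. This agrees with the Combination Phase header of Table 1 (weeks 0 to 24), so the text and the table header are consistent with each other.

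**2. The Table 1 row.** The temozolomide row has 13 marks. The excess over the text is 13 − 6 = 7. If each mark is one 28-day cycle, 13 × 28 = 364 days = 52 weeks, against 24 weeks in the text.

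**3. Where the marks fall.** Taking the printed columns at face value, mark k falls at week 4 × (k − 1):

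| Weeks | Marks | Relation to the text |
|---|---|---|
| 0, 4, 8, 12, 16, 20 | 6 | the six cycle starts |
| 24 | 1 | a seventh start, when six cycles have already ended |
| 28, 32, 36, 40, 44, 48 | 6 | in the Monotherapy columns |

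Total: 6 + 1 + 6 = 13.

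**4. Does this depend on column alignment?** The count does not. The conclusion that the row enters the Monotherapy columns needs only the four-weekly spacing. Weeks 0 to 24 hold at most 24/4 + 1 = 7 four-weekly marks, so at least 13 − 7 = 6 lie beyond week 24 wherever the row starts. If the empty cells between marks were an artefact of reading the table, 13 consecutive marks would fill the 24/2 + 1 = 13 two-weekly columns of the Combination Phase. That would be a two-weekly pattern, still 13 against 6. The avelumab row of the same table is read with 26 consecutive marks and no gaps, which supports the alternating reading for temozolomide.

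**5. Start interval.** Four weeks = 4 × 7 = 28 days, and 28 − 21 = 7 days beyond the limit in 4.2. Two readings of the limit differ:

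- Section 4.2 limits the break before the Combination Phase itself, so no start date satisfies both 4.2 and Appendix 4.
- Exclusion 6 limits only the time to baseline. With the allowance in 9.2, the latest first dose is 21 + 7 = day 28, which just meets Appendix 4.

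**The case against.** **Table 1 is a slip against a clear rule.** The text is unanimous on six cycles, Table 1's own header separates the two phases, and 4.2 defines Monotherapy as what follows completing or stopping temozolomide. Staff who read the body would not be misled. This stands as a reason to treat seven extra cycles as a worst case. It does not remove the contradiction in the schedule that section 9 points to.

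**Exact weeks are uncertain.** Read in the same way, the physical examination marks fall at weeks 26, 36 and 46, although 9.3.2 sets examinations every 12 weeks after the first 12 weeks. This is fair, and the week-by-week placement should not be pressed. The count of 13 does not depend on it.

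**Appendix 4 is not the study's start rule.** It is a monograph extract that also contains dosing for recurrent glioma, and the body cites it only for adjusting or withholding the dose. The 21-day limit is repeated consistently in the Synopsis, 4.1, 4.2 and the entry criteria. This largely stands, and it makes the start interval a secondary point. A reader might infer that every patient starts at least 7 days before the Appendix 4 time. The exclusion 6 reading, with the allowance in 9.2, does not support that.

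**Consequences can be overstated.** A reader might infer that events in the Monotherapy Phase could not be attributed at all. Section 11.1.3 already requires a judgement for each drug, including throughout the Combination Phase, so extra temozolomide makes attribution harder, not impossible.

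**Conclusion.** The inconsistency is real and should be corrected. Table 1 shows 13 temozolomide marks where the text has six cycles, a difference of 7. At the printed four-weekly spacing, at least 6 of the 13 marks fall in the Monotherapy columns. Seven extra cycles is the most that could follow if staff worked from the table alone. It is not a forecast of what will be given. The conclusion rests on the count of marks and, for the overlap with Monotherapy, on the alternate-column spacing.

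The start-interval conflict (21 days against 28) is real on the wording of 4.2 and Appendix 4 but secondary, because Appendix 4 is not cited for the start.

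Two further inferences are tempting but unsupported:

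- **Time zero for OS and PFS is not in doubt.** Both endpoints run from baseline (5.2 and 12.3.2), whatever Appendix 4 says.
- **No analysis treats the Monotherapy Phase separately as avelumab alone.** Neither Protocol section 12 nor the SAP plans an analysis by phase. What is at stake is exposure in a phase defined as monotherapy and the judgement of relatedness behind the primary endpoint.

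**What to change.** 1. Reconcile the temozolomide row of Table 1 with the number of cycles in 4.2 and 10.1, and add a footnote saying when temozolomide ends.
2. State at the head of Appendix 4 which of its parts apply to this study. Reconcile its start interval with 4.2, exclusion 6 and the allowance in 9.2, so that one interval governs and it is clear whether it runs to the baseline visit or to the first dose.

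The sponsor's clinicians decide the number of cycles and the interval. If the number of cycles in the text changes, the covariate for completing six cycles in Protocol 12.3.3 and SAP 1.3.3 must follow.

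The cost is protocol and table wording, submitted as an amendment under 15.2. The sample size and the planned analyses are unaffected if the text's count is kept.

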**Table 8. TEMODAL® Dose Levels for Maintenance Treatment**

Dose Level	Dose (mg/m2/day)	Remarks
-1	100	Reduction for prior toxicity
0	150	Dose during Cycle 1
1	200	Dose during Cycles 2–6 in absence of toxicity

**Table 9. TEMODAL® Dose Reduction or Discontinuation During Maintenance Treatment**

Toxicity	Reduce TEMODAL® by 1 Dose Levela	Discontinue TEMODAL®
Absolute Neutrophil Count	<1.0 x 10 9 /L	See footnote b
Platelet Count	<50 x 10 9 /L	See footnote b
CTC Non-hematological Toxicity (except for alopecia, nausea, vomiting)	CTC Grade 3	CTC Grade 4b

a: TEMODAL® dose levels are listed in Table 8.

b: TEMODAL® is to be discontinued if dose reduction to <100 mg/m2 is required or if the same Grade 3 non-hematological toxicity (except for alopecia, nausea, vomiting) recurs after dose reduction.

CTC = Common Toxicity Criteria.

#### **Malignant Gliomas Showing Recurrence or Progression after Standard Therapy:**

Adult patients: In patients previously untreated with chemotherapy, TEMODAL® is administered at a dose of 200 mg/m2 once daily for 5 days per 28-day cycle. For patients previously treated with chemotherapy, the initial dose is 150 mg/m2 once daily for 5 days, to be increased in the second cycle to 200 mg/m2 once daily for 5 days, providing there is no hematologic toxicity (see **WARNINGS AND PRECAUTIONS**). In the reference controlled trial of GBM, the majority of patients treated with TEMODAL® (90%) received more than one cycle and 22% of patients received 6 or more cycles. These patients received a total of 484 cycles of TEMODAL® in total; 60% of cycles at 200 mg/m2/day and 36% at 150 mg/m2/day. In the single arm AA trial, 93% of patients received more than one cycle and 25% of patients continued on study for 12 months or greater. Eighty-eight percent of patients were receiving either their initial dose or a higher dose at the last cycle. However, limited experience is available on the prolonged use of TEMODAL® in this patient population.

TEMODAL® therapy can be continued until disease progression.

## APPENDIX 5:

### ECOG PERFORMANCE STATUS

These scales and criteria are used by doctors and researchers to assess how a patient's disease is progressing, assess how the disease affects the daily living abilities of the patient, and determine appropriate treatment and prognosis. They are included here for health care professionals to access.

ECOG PERFORMANCE STATUS*	
Grade	ECOG
0	Fully active, able to carry on all pre-disease performance without restriction
1	Restricted in physically strenuous activity but ambulatory and able to carry out work of a light or sedentary nature, e.g., light house work, office work
2	Ambulatory and capable of all selfcare but unable to carry out any work activities. Up and about more than 50% of waking hours
3	Capable of only limited selfcare, confined to bed or chair more than 50% of waking hours
4	Completely disabled. Cannot carry on any selfcare. Totally confined to bed or chair
5	Dead

\* As published in Am. J. Clin. Oncol.: Oken, M.M., Creech, R.H., Tormey, D.C., Horton, J., Davis, T.E., McFadden, E.T., Carbone, P.P.: Toxicity and Response Criteria Of The Eastern Cooperative Oncology Group. Am J Clin Oncol 5:649-655, 1982.

1. STATISTICAL STATEMENT AND ANALYTICAL PLAN

1.1. Sample Size Considerations

A convenience sample of thirty (30) patients is based on recruitment feasibility. This sample size will permit estimation of dichotomous outcome rates with margins of error of less than 18% (based on a significance level of 0.05) and estimation of continuous parameter means to within 0.36 standard deviations. This is an early stage study, so analysis will focus on descriptive statistics. Continuous parameters will be summarized by means and 95% confidence intervals or by medians and interquartile ranges, as appropriate. Dichotomous outcomes will be summarized with point estimates of the rate, as well as 95% confidence intervals. Time-to-event data will be summarized using Kaplan-Meier curves.

1.2. Analyses

Complete analysis will be done when all patients have completed week 52 or end of study visit and repeated every 52 weeks thereafter. Interim descriptive analyses will be done when the first 10 patients have completed week 52 or the end of study visit and repeated when the first 20 patients have done so as well.

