### **Endpoints**

Complete data analysis will be done when all patients have completed the week 52 visit and repeated every 52 weeks thereafter.

Interim descriptive analyses will be done when the first 10 patients have completed week 52 visit and repeated when the first 20 patients have do so as well.

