#### **Analyses**

Complete analysis will be done when all patients have completed week 52 visit and repeated every 52 weeks thereafter. Interim descriptive analyses will be done when the first 10 patients have completed week 52 visit and repeated when the first 20 patients have done so as well.

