### **9.3.4. Assessments at end of study**

An end of treatment study visit will occur when:

- 1) Grade 3 or higher avelumab related toxicity occurs
- 2) Evidence as per the iRANO criteria of tumor progression occurs and patient does not wish to continue treatment
- 3) Patient wishes for any reason to discontinue treatment or withdraw from the study. Clinical evidence of neurological deterioration resulting in an ECOG score

of at least 3 or more, unexplained by other comorbidities, unchanged by an increase in corticosteroid dose and sustained for at least two weeks.

A history, physical and neurological exam will be performed by a physician. Laboratory test as per schedule will be drawn. If any of the latter have already been performed to confirm the AE or tumor progression on the basis clinical neurological deterioration, then they need not be repeated.

A study specified gadolinium enhanced MRI or CT scan will be performed within 2 weeks of the end of study visit for all patients after 52 weeks.

Patients however who discontinue the study treatment on the basis of avelumab treatment related AE's or clinical evidence of tumor progression a study specified MRI or CT scan will be done at the discretion of the investigator.

Patients who prematurely discontinue study treatment will be encouraged to continue into the Extended Safety Follow-up phase of the study

Patients who not only end treatment but also withdraw from the study, for any reason, will be encouraged to have telephone follow ups every month in order to obtain survival information with regards to OS. Pathology samples will be obtained for repeat biomarker analysis if a second tumor surgery occurs

**NOTE:** Since the actual duration of pseudoprogression and the time for immunotherapies to become effective in patients with GBM are still unknowns patients will be allowed at the investigator and patient discretion to continue on study treatment after confirmation of radiographic progression unless there is significant drug toxicity Grade 3 or higher AE's unrelated to avelumab such as those secondary to intercurrent illness or temozolomide therapy do not constitute for the purpose of this study a reason to withhold avelumab therapy or withdraw the patient from the study.

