### **9.3.7. Follow-up**

All patients who discontinue from study treatment will be followed for survival information.

In addition, patients who withdraw from study treatment as a result of progressive disease all further anti-neoplastic treatment, (including surgery and re-irradiation) will be recorded until death or end of the study whichever occurs first.

Survival telephone visits will be performed every 4 weeks until death or the end of the study, whichever occurs first.

For patients who prematurely withdraw from study treatment without documented disease progression:

Disease assessments will be performed until disease progression is observed. All further anti-neoplastic treatment (including surgery and re-irradiation) will be recorded until death or end of the study whichever occurs first. Telephone survival visits will be performed every 4 weeks until death or the end of the study, whichever occurs first.

If the patient withdraws consent, this request must be documented in the source documents, and signed by the investigator. At this time, the patient will be asked if he/she agrees to be followed-up for collection of survival information. This agreement must be documented and signed by the investigator. The study staff may also use a public information source to obtain information about survival status.

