1.3.2. Secondary Endpoints

Based on the results of Stupp *et al* (2005) (3), if avelumab had no effect then we would expect to see one-year overall survival and progression-free survival rates of 60% and 27%, respectively. We will conclude that we have preliminary evidence of benefit if either of our observed rates is significantly better based on a one-sided t-test at the 0.2 level of significance. With our projected sample of 30, this corresponds to concluding benefit if at least 21 patients survive to one-year or if at least 11 have survived without progression of disease.

Radiological tumor response will be graded according to the immunotherapy Response Assessment for Neuro-Oncology (iRANO)

Progression of Disease (PD) will be defined as a $\geq 25\%$ increase on the 12 month MRI or CT scan in the sum of the product of the biperpendicular diameters of enhancing disease; or new lesions; or substantial worsened T2/FLAIR; or significant clinical neurological decline unexplained by a change in medication or concurrent comorbidities. The SPD is the sum of the products of biperpendicular diameters of the measurable enhancing lesions (max 5 lesions).

Complete Response (CR) will be defined as the disappearance on the month 12 MRI or CT scan of all enhancing disease, no new lesions, with stable or improved T2/FLAIR; no more than physiological steroids; clinically stable or improved

Partial Response (PR) will be defined as a $\geq 50\%$ decrease on the month 12 MRI or CT scan in the sum of the product of the biperpendicular diameters of enhancing disease, no new lesions, stable or improved T2/FLAIR, stable (>2 months) or decreased steroid dose, clinically stable or improved

Stable Disease (SD) will be defined at 12 months when a patient do not qualify for complete response, partial response, or progressive disease, stable or improved T2/FLAIR; stable (>2 months) or decreased steroid dose, clinically stable or improved

Overall survival (OS) will be defined as the time from baseline to the date of death from any cause.

Objective Response Rate (ORR) will be defined the number of patients with either CR or PR divided by the total number of patients.

Progression Free Survival (PFS) will be defined as the time from baseline to documented PD or death from any cause.

Results will be stratified according to MGMT status, baseline age (>50 yrs), baseline Karnofsky performance score (score of 100), radical tumor resection vs biopsy, primary versus secondary GBM,

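### The complete analysis can start before every patient has one year of follow-up, so the one-year survival count against 21 of 30 may include patients whose status is not yet known

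*SAP*

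**What the plan says.** **Complete analysis.** SAP 1.2: "Complete analysis will be done when all patients have completed week 52 or end of study visit", with a repeat every 52 weeks. Protocol 6.1 and 12.2 agree. The protocol synopsis does not offer the end-of-study alternative: "Complete analysis will be done when all patients have completed week 52 visit and repeated every 52 weeks thereafter" (Analyses) and "Complete data analysis will be done when all patients have completed the week 52 visit" (Endpoints).

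**Interim looks.** SAP 1.2: "Interim descriptive analyses will be done when the first 10 patients have completed week 52 or the end of study visit", and again at 20 patients. They are called descriptive and carry no decision rule.

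**The end-of-study visit.** Protocol 9.3.4, headed as end-of-study assessments, begins "An end of treatment study visit will occur when". It lists grade 3 or higher avelumab toxicity, progression in a patient who does not wish to continue, the patient's wish to stop or withdraw, and sustained neurological decline to ECOG 3 or worse. Protocol 9.3.8 places the visit at week 260 or at progression.

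**What the analysis decides.** SAP 1.3.2 concludes preliminary benefit if "at least 21 patients survive to one-year" or if at least 11 are alive without progression, out of 30. It does not say how a patient with unknown one-year status is counted.

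**Follow-up after stopping.** Protocol 9.3.7: "Survival telephone visits will be performed every 4 weeks until death or the end of the study, whichever occurs first". Patients who stop without progression also continue disease assessments.

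**The concern.** The benefit rule needs each patient's status at 52 weeks from baseline. The trigger does not guarantee 52 weeks from baseline. A patient who stops at week 10 has met it at week 10. If that patient is the last enrolled and everyone else has met theirs, the analysis may start with 52 − 10 = 42 weeks of that patient's first year still to run.

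Someone must then decide, with the data in hand, whether such a patient counts towards the 21. The plan does not say. With a sample of 30 and a fixed cut-off, that choice can settle whether preliminary benefit is declared. The synopsis is no way out, because its trigger is different and in practice unreachable.

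**Working it through.** **1. The plan's own cut-offs.** Inputs from SAP 1.1 and 1.3.2: n = 30, null one-year OS 60%, null one-year PFS 27%, one-sided 0.2. Exact binomial tails:
- OS: P(X ≥ 21 | 30, 0.60) = 0.176; P(X ≥ 20) = 0.291.
- PFS: P(X ≥ 11 | 30, 0.27) = 0.161; P(X ≥ 10) = 0.276.

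The t-test named in the SAP, t = (p̂ − p0)/√(p̂(1 − p̂)/29), gives p = 0.125 at 21 and 0.226 at 20, and 0.144 at 11 and 0.238 at 10. Both cut-offs reproduce.

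**2. When status is unknown.** For patient i let e be the calendar week of baseline, and s and d the weeks from baseline to the stopping visit and to death. The patient meets the trigger at e + min(s, d, 52). The wording does not cover a patient who dies without either visit; I let death count. The analysis time T is the latest of the 30. One-year status is unknown at T if T − e < 52 and d > T − e.

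**3. How often.** Assumptions, with sources:
- OS: Weibull through 60% at 52 weeks (SAP 1.3.2) and 27% at 104 weeks (Protocol 1.1.1). Shape = log2(ln 0.27 / ln 0.60) = log2(1.309/0.511) = 1.36.
- PFS: exponential, 27% at 52 weeks (SAP 1.3.2).
- Not in the documents: uniform accrual over 52, 104 or 156 weeks; 50 to 100% of patients stopping at progression; correlation 0.6 between progression and death. The ends of the ranges move somewhat with the form of that dependence.

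A second model uses exponential exit from treatment, with 44% or 27% alive and on treatment at 12 months, a low death rate before exit, and a post-exit rate set so that one-year OS is 60%.

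| At the complete-analysis trigger | Progression model | Exit model |
|---|---|---|
| Mean patients with unknown one-year OS, of 30 | 0.5–1.6 | 0.4–1.2 |
| Chance of at least one | 34–70% | 29–58% |
| P(≥ 21) under no effect, full follow-up | about 0.18 | 0.17–0.18 |
| same, unknowns counted as alive | 0.18–0.20 | 0.18–0.20 |
| same, unknowns counted as not surviving | 0.09–0.15 | 0.11–0.16 |
| Mean delay if every patient is given 52 weeks | 2–10 weeks | 0.4–2.0 months |

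**4. The PFS count.** A patient who stops at progression is already a known PFS failure. The count against 11 can be incomplete only for patients who stop for toxicity or by choice without progression. The progression model does not include them, so no figure is given.

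**5. The synopsis trigger.** Read literally, every patient must attend week 52. At the plan's own 60% survival, and taking patients as independent, the chance that all 30 are even alive then is 0.6^30, about 2 in 10 million.

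**6. The interim sets.** If the first 10 or 20 are taken in enrolment order, expected one-year OS in the set is 60%. If they are the first to reach the trigger, true one-year OS is 0.32–0.51 in the first 10 and 0.48–0.55 in the first 20 (progression model), or 0.24–0.50 and 0.45–0.55 (exit model). The SAP does not say which is meant.

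**The case against.** The strongest reply is that the plan already contains the safeguards. A patient alive at week 40 has not survived to one year, so on a strict reading is not counted. Survival calls run every four weeks, Protocol 5.2 defines censoring, SAP 1.1 provides Kaplan-Meier curves, and the analysis is repeated 52 weeks later, when all 30 have a year of potential follow-up. Progression brings the visit only if the patient declines to continue, and continuation is offered. The endpoint is secondary, in a descriptive study whose primary endpoint is safety.

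Much of this stands and limits the size. It does not remove the point. The benefit rule is a raw count, not a Kaplan-Meier estimate. The strict reading turns patients who may well reach one year into failures, which lowers the chance of reaching 21. The repeat comes after a conclusion has been drawn and may contradict it. The calls show that the data will exist; the analysis need only wait.

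A reader might infer three stronger things that the documents do not support:
- *Interim survival is biased low.* This follows only if the first 10 or 20 means first to reach the trigger. In enrolment order there is no selection. With no decision rule attached, the harm is misleading description, not type I error.
- *Both counts are equally exposed.* Patients who stop at progression have known PFS status.
- *One patient moves the false-positive rate from 0.18 to 0.29.* Those are the tails for cut-offs of 21 and 20. The trigger's own effect is in the table: at most about 0.02 upward, which keeps the rate at about the nominal 0.2, and more downward.

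**Conclusion.** The point holds for the complete analysis and the OS count. As written, the trigger allows the comparison with 21 before one-year status is known for late-enrolled, early-stopped patients, and the plan has no rule for them. The likely number is small, from none to a few of 30. The larger distortion is downward, where unknowns count as not surviving. These sizes rest on accrual and stopping patterns that the documents do not state, although two differently built models give similar ranges.

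The PFS count is exposed only through stops without progression. The interim concern depends on a reading that the SAP leaves open. The conflict between the synopsis and the other sections stands regardless of any modelling. This is a modest defect on a secondary endpoint, worth correcting because the repair is cheap.

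**What to change.** Use one trigger in the synopsis (Endpoints and Analyses), Protocol 6.1 and 12.2, and SAP 1.2:
- Complete analysis: 52 weeks after the last enrolled patient's baseline, then every 52 weeks.
- Interim looks: 52 weeks after the baselines of the 10th and 20th enrolled patients, on exactly the first 10 or 20 enrolled, whatever their treatment status.
- Counts: state in SAP 1.3.2 how a patient lost before one year enters the counts against 21 and 11.

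Do not adopt the synopsis wording in place of the SAP's. The cut-offs of 21 and 11 do not change. The cost is wording and an average delay of about 2 to 10 weeks under the assumptions above. No added patients, visits or procedures are needed, since Protocol 9.3.7 already provides for the follow-up.
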